#### 4.1.1.2. Dose-Limiting Toxicity Criteria

DLT is defined as any one of the following toxicities considered by the investigator to be related to study treatment:

- Grade  $\geq 4$  adverse events (AEs)
- Grade 3 febrile neutropenia or hemorrhage
- Grade 3 thrombocytopenia with clinically significant bleeding
- Grade 3 non-hematologic AEs, including rash, nausea/vomiting, hypertension, diarrhea, retinopathy, or blurred vision that remain uncontrolled (does not resolve to  $\leq$  Grade 2) for

>72 hours despite maximal supportive care. Electrolyte abnormalities or Grade 3 asymptomatic CPK or GGT elevations that is corrected within 72 hours will not be considered DLTs.

- Grade 3 AST, ALT, and/or total bilirubin elevations that persist >5 days
- Concurrent elevation of AST or ALT  $>3 \times$  ULN **AND** total bilirubin  $>2 \times$  ULN or international normalized ratio (INR)  $>1.5$  in the absence of cholestasis and other causes (eg, viral hepatitis, other pre-existing or acute liver disease, or another drug capable of the observed injury), which may indicate severe drug-induced liver injury (possible Hy's law case)
- Grade 3 QTcF (defined as QTc using Fridericia's formula [QTcF]  $>500$  msec OR change from baseline of QTcF  $>60$  msec) prolongation based on a triplicate ECG
- Retinal vein occlusion (RVO) any grade
- 50% or less dose intensity of RMC-4630 (eg, miss  $\geq 4$  doses) and/or cobimetinib (eg, miss  $\geq 10$  doses if cobimetinib is dosed daily during 21/7 schedule or miss  $\geq 4$  doses if cobimetinib is dosed intermittently on D1, D2) due to study drug related toxicity
- Ejection fraction  $<50\%$  with an absolute decrease of  $>10\%$  from baseline

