## Overall Design

This study arm with RMC-4630 and cobimetinib will be conducted in US and ex-US countries. This arm includes two components: a Dose-Escalation Component and a Dose-Expansion Component. The overall schema is illustrated in [Figure 1](#).

Prior to enrollment, all participants will undergo screening based on prior genomic testing using a clinically validated or qualified assay on either tumor tissue or circulating tumor DNA (ctDNA) samples. Questions regarding eligible mutations may be addressed to the Sponsor. Participants with at least one the following genotypes and histotypes will be enrolled

[REDACTED]

[REDACTED]

[REDACTED]

[REDACTED]

[REDACTED]

[REDACTED]

[REDACTED]

Archival tissue will be requested from all participants. For genomic reports based on clinically validated local tests and used for enrollment, retrospective analysis will be performed by a central lab on archival tissue for analysis and reporting purposes. A fresh biopsy will not be used to determine patient eligibility.

***Dose-Escalation Component:*** This arm will begin with the Dose Escalation Component. The initial dose of RMC-4630 will be 80 mg administered orally (PO) twice weekly, D1 and D4, for 28 days of a 28-day cycle.

The starting dose of cobimetinib will be 20 mg PO administered daily (QD) on days 1-21 of a 28-day cycle (21/7 schedule). This dose is two dose levels below the approved dose of cobimetinib of 60 mg PO QD on the 21/7 schedule.

In addition to the planned dose levels, alternative dose schedules which allow D1, D2 dosing of either or both RMC-4630 and cobimetinib may be initiated and the starting dose will be based on the analysis of emerging safety and PK data. Therefore, RMC-4630 can be administered in either a D1, D4 or D1, D2 schedule. Whereas, cobimetinib can be administered in either once daily (21/7) or D1, D2 schedule. However, the single and monthly starting dose for cobimetinib will not exceed those already tested in clinical trials. The decision to trigger exploration of an alternative schedule will be made by the Dose-Escalation and Expansion Committee (also referred to as “Dose Committee”) after careful review of emerging toxicity profile of the combination.

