#### 4.1.1.3. Dose-Escalation Rules

Dose escalation will be guided using a CRM model ([Appendix 10](#)) to determine the MTD of the combination of RMC-4630 and cobimetinib. This CRM is an adaptive dose escalation approach based on a Bayesian statistical model to assess the MTD for drug combinations as a function of their doses. [REDACTED]

[REDACTED] The MTD is selected as the combination associated with the highest posterior probability of DLT rating within the target interval of 25% - 35% with a target DLT rate of 30%, and which have been used to treat at least 6 participants. If alternative dosing schedule(s) are evaluated, a separate CRM model will be set up using the same modeling structure but potentially different parameters according to the updated prior knowledge of the safety of the alternative dosing schedule(s).

During the escalation period, participants will be enrolled in a series of cohorts for each combination dose level. A minimum of 3 participants are required on a combination dose level to be DLT evaluable and to render a decision to proceed to the next dose level. A 4th participant, if available, may enroll onto the escalation dose before the first 3 participants have completed the DLT evaluation. However, in the case a 4th patient is enrolled in a cohort, dose escalation decision will take place after the first 3 patients have completed the DLT assessment period.

Once the DLT status of the 4th patient is available, and if this patient experiences a DLT after dose escalation decision and enrollment of the subsequent dose level, the Sponsor will rerun the Bayesian model and the Dose Committee will re-evaluate the dose escalation recommendation and continuation of treatment at the subsequent dose level. If a participant experiences a DLT, additional participants will be enrolled at that dose. The cohort at the MTD will include at least 6 participants.

A participant will be DLT non-evaluable in either of the following 2 scenarios where a replacement participant(s) will be enrolled:

1. Receives less than 75% of planned dose of cobimetinib (miss  $\geq 3$  doses of cobimetinib on DID2 intermittent schedule and  $\geq 6$  doses of cobimetinib on 21 on/7 off schedule within the DLT window) for reasons other than toxicity
2. Misses 3 or more consecutive or non-consecutive doses of RMC-4630 within the DLT window for reasons other than toxicity

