**4.2.1.3. Dose-Escalation Rules**

In the event a participant discontinues treatment prior to completion of the first cycle (DLT window), receives less than 75% of planned dose of osimertinib (defined as missing 8 or more consecutive or non-consecutive doses of osimertinib), receives less than 75% of planned dose of RMC-4630 (defined as missing 3 or more consecutive or non-consecutive doses of RMC-4630) for reasons other than toxicity, a replacement participant will be enrolled for a minimum of 3 DLT evaluable participants.

The Dose Committee will be responsible for reviewing and evaluating the safety, efficacy data and other relevant available information (PK or biomarker data) during the DLT period and provide a final decision regarding the next dose escalation level. The RP2D will be determined

by the Sponsor based on the totality of the information available at all dose levels and should not exceed the MTD. If 2 or more DLTs are observed beyond the DLT assessment period (ie, a delayed DLT) within a Dose-Escalation Cohort, further enrollment may be stopped pending safety analysis of the events. These events will not affect the determination of the MTD but will be used in determining the appropriate RP2D. Further details on the Dose Committee are provided in [Section 8.3.6](#). The Sponsor will determine regarding opening the Dose-Expansion Component.

The ISMC will conduct regular safety data reviews of emergent data from the RMC-4630 program as well as ad hoc emergent safety data reviews for all participants across RMC-4630 trials.

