### 6.1. Study Intervention(s) Administered

#### 6.1.1. RMC-4630 and Cobimetinib

[REDACTED]

In addition to the planned dose levels, alternative dose schedules which allow D1, D2 dosing of either or both RMC-4630 and cobimetinib may be initiated and the starting dose will be based on

the analysis of emerging safety and PK data. Therefore, RMC-4630 can be administered in either a D1, D4 or D1, D2 schedule. Whereas, cobimetinib can be administered in either once daily (21/7) or D1, D2 schedule. However, the single and monthly starting dose for cobimetinib will not exceed those already tested in clinical trials. The decision to trigger exploration of an alternative schedule will be made by the Dose Committee after careful review of emerging toxicity profile of the combination.

RP2DS for final expansion is RMC-4630 140 mg on D1D2 and cobimetinib 40 mg on D1D2.

The tablets and capsules should not be crushed or chewed. The participant should administer the study intervention approximately the same time every day except for clinic visit days as listed in the SoA (Section 1.3). On these clinic visits, the participant should await instruction from the study staff to coordinate with the timing of PK and/or PD sampling.

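### The DLT example for daily cobimetinib (10 or more of 21 doses missed) leaves 52.4% dose intensity and so does not meet the 50% rule it illustrates; the first count that does is 11

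*Combined protocol and SAP*

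**What the plan says.** Section 4.1.1.2 lists the DLT criteria for the cobimetinib arm. One of them is "50% or less dose intensity of RMC-4630" and/or cobimetinib, when the cause is study-drug toxicity. Each drug has a worked count introduced by 'eg': 4 or more missed doses for RMC-4630, and for cobimetinib 10 or more "doses if cobimetinib is dosed daily during 21/7 schedule or miss" 4 or more on the D1, D2 schedule.

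The synopsis (Overall Design, cobimetinib arm) sets the number of planned doses. Cobimetinib starts at "20 mg PO administered daily (QD) on days 1-21 of a 28-day cycle (21/7 schedule"), which is 21 doses per cycle. The DLT window is Cycle 1, 28 days (section 4.1.1.1).

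A separate rule in section 4.1.1.3 uses the same schedule. A participant who receives less than 75% of planned cobimetinib for reasons other than toxicity is not DLT-evaluable, and this is counted as missing 6 or more "doses of cobimetinib on 21 on/7 off schedule within the DLT window". The osimertinib arm has parallel rules: 14 or more missed doses for the 50% DLT criterion (section 4.2.1.2), and for evaluability a 75% rule "defined as missing 8 or more consecutive or non-consecutive doses of osimertinib" (section 4.2.1.3).

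**The concern.** An example should satisfy the rule it illustrates, and here it does not. Because the count is only an example, a reader can take the percentage as governing. A site or programmer who wants an operational threshold will more naturally take the count. The two readings disagree for a 21/7 participant who misses exactly 10 doses for drug-related toxicity and meets no other DLT criterion.

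The classification has consequences. DLT incidence is a primary endpoint (section 3.1) and the DLT rate is part of the primary safety analysis (Table 17). DLTs are the input to the CRM. Section 4.1.1.3 also ties an action to a single event: "If a participant experiences a DLT, additional participants will be enrolled at that dose".

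**Working it through.** **Inputs.**
- Planned doses in the 28-day window: cobimetinib 21/7, once daily on days 1 to 21, n = 21; RMC-4630 twice weekly, or cobimetinib on D1, D2, n = 2 × 4 weeks = 8; osimertinib once daily, n = 28.
- Thresholds: 50% or less for a DLT; less than 75% for non-evaluability.
- Section 6.6.1 bars dose reductions in Cycle 1 of escalation unless a DLT has occurred, so dose intensity can be measured by counting doses.

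**Formula.** With m doses missed, dose intensity = (n − m)/n. A count matches its rule if m is the smallest whole number at which the rule is met, that is, the rule is met at m and not at m − 1.

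**Results.**

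| Rule | n | Stated m | At m | At m − 1 | Matches? |
|---|---|---|---|---|---|
| DLT, ≤50%: RMC-4630 | 8 | 4 | 4/8 = 50.0% | 5/8 = 62.5% | yes |
| DLT, ≤50%: cobimetinib D1, D2 | 8 | 4 | 4/8 = 50.0% | 5/8 = 62.5% | yes |
| DLT, ≤50%: osimertinib | 28 | 14 | 14/28 = 50.0% | 15/28 = 53.6% | yes |
| **DLT, ≤50%: cobimetinib 21/7** | **21** | **10** | **11/21 = 52.4%** | 12/21 = 57.1% | **no** |
| Non-evaluable, <75%: RMC-4630, or cobimetinib D1, D2 | 8 | 3 | 5/8 = 62.5% | 6/8 = 75.0% | yes |
| Non-evaluable, <75%: cobimetinib 21/7 | 21 | 6 | 15/21 = 71.4% | 16/21 = 76.2% | yes |
| Non-evaluable, <75%: osimertinib | 28 | 8 | 20/28 = 71.4% | 21/28 = 75.0% | yes |

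For 21/7 cobimetinib the first count that meets the 50% rule is m = 11, which leaves 10/21 = 47.6%.

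**Could another denominator rescue the figure?** Missing 10 reaches 50% only if 20 or fewer doses are planned: (20 − 10)/20 = 50.0%. The protocol plans 21. Using all 28 days gives 18/28 = 64.3%, which is further away.

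**Could it be a rounding convention?** A quarter of 21 is 5.25, and the protocol uses 6. Half of 21 is 10.5, and the protocol uses 10. Rounding up, as in the first case, gives 11 in the second.

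**Size in a cohort.** In the minimum cohort of 3, one participant with exactly 10 missed doses and no other DLT changes the tally from 0/3 to 1/3.

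**The case against.** The arithmetic is not in dispute. The case on the other side concerns weight and remedy.

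*The percentage is the rule and the count is only an example.* Half of 21 is not a whole number, so the example may just be 10.5 rounded down, and an example does not normally override its rule. That is a fair reading of the text. It does not remove the problem, because a count that fails its own rule can still be the one a site applies.

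*Few participants can be affected.* Section 6.6.1 allows no dose modification in Cycle 1 of escalation unless a DLT has occurred, and it names interruption as a type of modification. Read literally, a participant whose drug was held already has a DLT. Other criteria also catch many long holds, such as uncontrolled Grade 3 non-hematologic events beyond 72 hours and Grade 3 liver abnormalities beyond 5 days. This does narrow the group, but it does not empty it. Doses can be lost to vomiting or prolonged Grade 2 toxicity. A Grade 3 event that falls to Grade 2 within 72 hours is not a DLT under its own criterion, yet section 6.6.2 holds drug until Grade 1 or better. Expansion data are also pooled into the model (section 4.1.1.3).

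*The consequence is limited.* The count is the more cautious reading and can only add a DLT. The Dose Committee, not the model, sets the dose. Alternative schedules have their own CRM model. Section 6.1.1 already states the outcome: "RP2DS for final expansion is RMC-4630 140 mg on D1D2 and cobimetinib 40 mg on D1D2", where 4 of 8 is exactly 50%. All of this stands, and it is why the point is minor.

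*Moving to 11 loosens a safety criterion after the dose has been chosen*, and could remove a DLT already counted. This stands too. The documents do not show whether 10 or 50% was the intended rule, so 11 is the count consistent with the percentage, not necessarily the intended one.

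**Conclusion.** The mismatch is real and the concern holds. The 21/7 example is one dose short of the rule it illustrates: 10 missed doses leave 52.4%, and 11 are needed to reach 50% or less. It is the only dose-intensity count in the protocol that fails its percentage.

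Severity is minor. One missed-dose value (exactly 10 of 21) is affected, on one schedule, and only when no other DLT criterion is met. This rests on 21 planned doses in Cycle 1 and on dose intensity being doses taken over doses planned, with no reduction in dose size.

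Two things cannot be established from the documents: how many participants, if any, fall in this group, and what a reclassified DLT would do to the CRM recommendation, since the model's priors are not available. Nothing here implies that the MTD, the final-expansion dose or the DLT incidence is wrong.

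**What to change.** Choose one rule for 21/7 cobimetinib in section 4.1.1.2:
- change the count from 10 to 11, so that it agrees with 50% or less; or
- if the cautious count was intended, say that 10 or more missed doses governs on 21/7 in place of the percentage. This option avoids loosening a safety criterion now that the final-expansion dose has been named.

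Make the choice before looking at the data. Then check the Cycle 1 dosing records of 21/7 participants for anyone who missed exactly 10 cobimetinib doses for drug-related toxicity with no other DLT, and score any such participant under the chosen rule. If 21/7 escalation has finished, a single rule is still needed to report DLT incidence for those cohorts.

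The cost is one number or one clause, plus a short look-up.

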#### 4.1.1.3. Dose-Escalation Rules

Dose escalation will be guided using a CRM model ([Appendix 10](#)) to determine the MTD of the combination of RMC-4630 and cobimetinib. This CRM is an adaptive dose escalation approach based on a Bayesian statistical model to assess the MTD for drug combinations as a function of their doses. [REDACTED]

[REDACTED] The MTD is selected as the combination associated with the highest posterior probability of DLT rating within the target interval of 25% - 35% with a target DLT rate of 30%, and which have been used to treat at least 6 participants. If alternative dosing schedule(s) are evaluated, a separate CRM model will be set up using the same modeling structure but potentially different parameters according to the updated prior knowledge of the safety of the alternative dosing schedule(s).

During the escalation period, participants will be enrolled in a series of cohorts for each combination dose level. A minimum of 3 participants are required on a combination dose level to be DLT evaluable and to render a decision to proceed to the next dose level. A 4th participant, if available, may enroll onto the escalation dose before the first 3 participants have completed the DLT evaluation. However, in the case a 4th patient is enrolled in a cohort, dose escalation decision will take place after the first 3 patients have completed the DLT assessment period.

Once the DLT status of the 4th patient is available, and if this patient experiences a DLT after dose escalation decision and enrollment of the subsequent dose level, the Sponsor will rerun the Bayesian model and the Dose Committee will re-evaluate the dose escalation recommendation and continuation of treatment at the subsequent dose level. If a participant experiences a DLT, additional participants will be enrolled at that dose. The cohort at the MTD will include at least 6 participants.

A participant will be DLT non-evaluable in either of the following 2 scenarios where a replacement participant(s) will be enrolled:

1. Receives less than 75% of planned dose of cobimetinib (miss  $\geq 3$  doses of cobimetinib on DID2 intermittent schedule and  $\geq 6$  doses of cobimetinib on 21 on/7 off schedule within the DLT window) for reasons other than toxicity
2. Misses 3 or more consecutive or non-consecutive doses of RMC-4630 within the DLT window for reasons other than toxicity

Moving to a higher dose of both agents is not allowed. Moving to a higher dose of one agent and a lower dose of the other agent is allowed. Skipping a dose level as specified above is not allowed, but intermediate dose levels of RMC could be explored. Parallel dose cohorts may be allowed if the collective safety data are supportive ([Appendix 10](#)). The data in both Dose-Escalation and Dose-Expansion Components ([Section 4.1.1](#), [Section 4.1.2](#)) will be combined to fit the model and determine the recommended dose combination to treat the next cohort of patients.

The Dose Committee will be responsible for evaluating the safety data during the DLT period and provide decisions regarding the actual dose escalation level based on safety data, updated model dose recommendations, and other relevant available information. The RP2D will be determined by the Sponsor based on the totality of the information available at all dose levels, combining the Dose-Escalation and Dose-Expansion Components, and should not exceed the MTD. The Dose Committee will determine regarding opening the Dose-Expansion Component.

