**Table 5 Primary Dose Levels for RMC-4630**

In addition to the planned dose levels, alternative schedules which allow D1, D2 dosing of either or both RMC-4630 and cobimetinib may be initiated and the starting dose will be based on the analysis of emerging safety and PK data. Therefore, RMC-4630 can be administered in either a D1, D4 or D1, D2 schedule. Whereas, cobimetinib can be administered in either once daily (21/7) or D1, D2 schedule. However, the single and monthly starting dose for cobimetinib will not exceed those already tested in clinical trials. The decision to trigger exploration of an alternative schedule will be made by the Dose Committee after careful review of emerging toxicity profile of the combination.

The first cycle (eg, 28 days) constitutes the DLT assessment period. The first participant in the initial combination dose level will be observed for the first 7 days of dosing prior to dosing additional participants in this cohort. Following this 7-day observation period, additional participants may be enrolled in the cohort. In subsequent combination dose level cohorts, participants may be enrolled concurrently.

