### 9.2. Sample Size Determination

Both arms of the study will include two components: a Dose-Escalation Component and a Dose-Expansion Component consisting of 6 genotypic/histotypic cohorts.

Doses for both RMC-4630 and cobimetinib will vary in dose escalation component of arm 1. Dose escalation recommendations will be conducted using a CRM model for RMC-4630 and cobimetinib arm ([Appendix 10](#)). [Table 1](#) illustrates sample size estimation based on “Scenario 1” depicted in [Figure 2](#). The study is expected to enroll approximately 144 participants as follows:

- Up to 42 participants during the Dose-Escalation Component, assumes 7 total combination dose cohorts (RMC-4630 dosed twice weekly on D1, D4 or D1, D2 with cobimetinib dosed once daily on 21/7 schedule; RMC-4630 and cobimetinib dosed twice weekly on D1, D2) with 3 to 6 participants per dose. The MTD cohort will enroll at least 6 participants.
- After reaching threshold of activity and achieving DLT clearance at a dose level, at least 24 additional participants may be enrolled during expansion prior to RP2D for a maximum 12 participants per dose level (assumes 4 combination dose expansion cohorts).

- Up to 90 participants (15 per class of mutation x 6 strata) will be enrolled at RP2D (combination dose level 4a). Assuming 12 participants are already enrolled during dose escalation and expansion into cohort that will be declared RP2D, additional 78 participants will be enrolled into RP2D cohort.

The primary objective of this study is safety evaluation. The objective the efficacy evaluation is to generate data which will enable a preliminary estimation of the treatment effect. The treatment effect will be interpreted in the clinical context of specific genotypes and histotypes. The target disease stabilization rate is 30%. If 5 out of 15 participants have achieved disease stabilization, the observed disease stabilization rate would be 33% where the lower limit of the 95% CI is 12%, which excludes a null rate of 10%. A sample size of 15 will provide preliminary evidence of efficacy of RMC-4630 and cobimetinib. Replacement of efficacy unevaluable participants at RP2D may be considered.

With a sample size of 144 study participants, the probability of observing 1 or more instances of a specific AE with a true incidence rate of 1%, 2%, or 5% is 76%, 95%, or >99%, respectively.

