**Table 15 Population Definitions**

Population	Description
Enrolled	All participants who sign an ICF and meet eligibility criteria
Treated	All participants who take at least 1 dose of study intervention
Evaluable	
Evaluable for DLT: All participants in the treated population who have completed the DLT period or who have discontinued due to AEs or death (unless relationship to RMC-4630 and cobimetinib can be ruled out) prior to the end of the DLT period. In addition, participants must receive at least 75% of planned dose (not miss <math>\geq 3</math> doses of RMC-4630 and cobimetinib on D1D2 intermittent schedule and <math>\geq 6</math> doses of cobimetinib on 21 on/7 off schedule, and <math>\geq 8</math> doses of osimertinib within the DLT window for reasons other than toxicity). This population will be the primary population for fitting the dose-toxicity model.
 
Evaluable for efficacy: All participants with measurable disease at baseline, who take at least 1 dose of study intervention and underwent one post-baseline response assessment or who die or had clinical progression prior to first post-baseline response assessment

Safety	All participants who take at least 1 dose of study intervention

Abbreviations: AE, adverse event; DLT, dose-limiting toxicity; ICF, informed consent form.

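### The dose-intensity DLT rule and the evaluability rule each count missed doses for one reason only, so a participant with mixed reasons can receive half or less of the planned dose and still be classed as evaluable and DLT-free

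*Combined protocol and SAP*

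**What the plan says.** Two rules deal with under-exposure in the DLT window.

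- **DLT rule.** Section 4.1.1.2 lists as a DLT "50% or less dose intensity of RMC-4630 (eg, miss" 4 or more doses), with examples for cobimetinib of 10 or more doses on 21/7 and 4 or more on D1, D2. All of these apply only if the cause is study-drug-related toxicity. Section 4.2.1.2 has the same criterion for the osimertinib arm: 4 or more RMC-4630 doses, or 14 or more osimertinib doses.
- **Evaluability rule.** Section 4.1.1.3 makes a participant non-evaluable who "Misses 3 or more consecutive or non-consecutive doses of RMC-4630 within the DLT window for reasons other than toxicity". The cobimetinib cut-offs are 6 or more doses (21/7) or 3 or more (D1, D2), again for non-toxicity reasons. Section 4.2.1.3 uses 3 or more RMC-4630 doses or 8 or more osimertinib doses, "for reasons other than toxicity, a replacement participant will be enrolled for a minimum of 3 DLT evaluable participants".

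Table 15 (Section 9.3) defines the DLT-evaluable population, the primary population for fitting the dose-toxicity model. It says that "participants must receive at least 75% of planned dose". The bracket that follows repeats the missed-dose cut-offs and limits them to non-toxicity reasons.

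**The concern.** Each rule looks at one cause of missed doses, and neither looks at total exposure. A participant who stays just below both cut-offs can have lost more than half the planned dose, partly through drug toxicity, and still count as a full observation of no DLT. This conflicts with the opening wording of Table 15 and with the purpose of both rules. Section 4.1.1.3 allows an escalation decision on 3 evaluable participants at a dose level, so one misclassified record can be one of the three at that level.

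**Working it through.** **Planned doses in the window.** Section 4.1.1.1: "The first cycle (eg, 28 days) constitutes the DLT assessment period".

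- RMC-4630: "twice weekly, D1 and D4, for 28 days of a 28-day cycle" (synopsis, Overall Design), so 2 × 4 = 8 doses.
- Cobimetinib 21/7: "administered daily (QD) on days 1-21 of a 28-day cycle (21/7 schedule"), so 21 doses.
- Cobimetinib D1, D2: Section 9.2 has "RMC-4630 and cobimetinib dosed twice weekly on D1, D2". This is taken as 8 doses, which agrees with the protocol equating 4 missed doses with 50%.
- Osimertinib once daily: 28 doses.

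**Reproducing the plan's cut-offs.** Received share = (planned − missed) / planned.

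- Evaluability, below 75%: RMC-4630, 3 missed gives 5/8 = 62.5% and 2 missed gives 75.0%. Cobimetinib 21/7, 6 missed gives 15/21 = 71.4% and 5 missed gives 76.2%. Osimertinib, 8 missed gives 20/28 = 71.4% and 7 missed gives 75.0%. All agree with the text.
- DLT, 50% or less: RMC-4630 4/8 = 50.0% and osimertinib 14/28 = 50.0% agree. Cobimetinib 21/7 with 10 missed gives 11/21 = 52.4%; 11 missed (47.6%) would be needed for 50% or less, so that example is one dose off its stated percentage.

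**Lowest exposure that meets neither rule.** Misses = (DLT cut-off − 1) for toxicity + (evaluability cut-off − 1) for other reasons.

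| Drug and schedule | Toxicity + other misses | Received | Lowest if toxicity only | Lowest if other reasons only |
|---|---|---|---|---|
| RMC-4630 | 3 + 2 = 5 of 8 | 3/8 = 37.5% | 5/8 = 62.5% | 6/8 = 75% |
| Cobimetinib 21/7 | 9 + 5 = 14 of 21 | 7/21 = 33.3% | 12/21 = 57.1% | 16/21 = 76.2% |
| Cobimetinib D1, D2 | 3 + 2 = 5 of 8 | 3/8 = 37.5% | 5/8 = 62.5% | 6/8 = 75% |
| Osimertinib | 13 + 7 = 20 of 28 | 8/28 = 28.6% | 15/28 = 53.6% | 21/28 = 75% |

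With a single reason, each rule keeps exposure above 50%. Only the mixture breaks through. For RMC-4630, the combinations at 50% or less are 2+2, 3+1 and 3+2.

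**How often (assumed rates).** The documents give no miss rates. Assume that each of 8 doses is independently missed for toxicity with probability a, or for another reason with probability b. Then

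P(t, o) = 8! / (t! o! (8−t−o)!) × a^t × b^o × (1−a−b)^(8−t−o).

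The share wanted is [P(2,2) + P(3,1) + P(3,2)] divided by the sum of P(t, o) over t ≤ 3, o ≤ 2.

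For a = 10%, b = 5%:

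- P(2,2) = 420 × 0.10² × 0.05² × 0.85⁴ = 0.00548
- P(3,1) = 280 × 0.10³ × 0.05 × 0.85⁴ = 0.00731
- P(3,2) = 560 × 0.10³ × 0.05² × 0.85³ = 0.00086
- Sum 0.01365; denominator 0.98919; share 1.4%.

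| Toxicity / other miss rate per dose | Evaluable, DLT-free, 50% or less of RMC-4630 | Of which the 3+2 case |
|---|---|---|
| 5% / 3% | 0.15% | 0.005% |
| 10% / 5% | 1.4% | 0.09% |
| 15% / 8% | 5.6% | 0.6% |
| 20% / 10% | 12.1% | 1.7% |

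The last pair means 8 × 0.30 = 2.4 doses missed on average, which is high.

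**The case against.** Several counter-arguments carry weight.

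- **Cycle 1 modifications.** Section 6.6.1 bars dose modifications in Cycle 1 of escalation cohorts unless a DLT has occurred, and counts interruption as a modification. Read strictly, three toxicity holds without a DLT should not arise there. But the dose-intensity DLT in Section 4.1.1.2 presupposes such holds. The bar names only escalation cohorts, while Section 4.1.1.3 also feeds expansion data into the model. The sections need reconciling; redacted bullets near the Section 6.6.1 text may bear on it.
- **The counts are examples.** In Section 4.1.1.2 the criterion is dose intensity, and the counts are introduced as examples. A committee could attribute a 3+2 shortfall to toxicity and call it a DLT. That is possible but is not written. In Section 4.2.1.2 the osimertinib count is a definition.
- **Table 15 might already set a total floor.** Its bracket limits the count to non-toxicity misses. A true total floor would also remove window-completers whose only DLT is dose intensity of 50% or less, so it can hardly be the intent. The wording is ambiguous.
- **The illustration is rough.** It assumes independent misses and ignores the other DLT criteria, which such toxicity may well meet, and the make-up dosing in Section 6.4.2.
- **Escalation is not mechanical.** The Dose Committee weighs all safety data (Sections 4.1.1.3 and 8.3.6).

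A reader might infer that the gap always understates the DLT rate. The documents do not show this: a participant who would have been DLT-free at full exposure introduces no error. A reader might also infer that exposure falls to about a third for every drug. That fits cobimetinib 21/7; RMC-4630 stops at 37.5% and osimertinib at 28.6%.

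**Conclusion.** The gap is real on the operative wording: mixed-reason misses can leave a participant with 50% or less of planned dose, evaluable and DLT-free, in both arms. It requires that no other DLT criterion is met. It is an uncommon edge case. The range of 0.15% to 12% rests wholly on assumed miss rates and independence, and the extreme 3+2 case is at most 1.7% within that range. It would be tempting to conclude that escalation decisions are materially biased. The documents do not support that, because the CRM details in Appendix 10 are redacted and the Dose Committee can override the model. What is established is a wrong evaluability classification that is cheap to prevent, together with two wording conflicts: within Table 15, and between Sections 4.1.1.2 and 6.6.1.

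**What to change.** 1. In Sections 4.1.1.3 and 4.2.1.3 and Table 15, state that a participant without a DLT whose total received dose of either drug in the DLT window is 50% or less, counting misses for all reasons together, is not DLT-evaluable and is replaced. List these participants separately, with their toxicity, for the Dose Committee so that the signal is not lost. Leave the DLT criteria unchanged.
2. Make the opening wording of Table 15 agree with its bracket.
3. Reconcile the Cycle 1 restriction in Section 6.6.1 with the dose-intensity DLT in Section 4.1.1.2.

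With the first change, an evaluable DLT-free participant has received at least 5/8 = 62.5% of RMC-4630, 11/21 = 52.4% of cobimetinib on 21/7 and 15/28 = 53.6% of osimertinib.

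A 75% floor on total dose for mixed-reason cases is a less suitable alternative. Three toxicity misses would stay evaluable while one toxicity plus two other misses, at the same 62.5%, would not. It would also remove about 7%, 19% and 31% of evaluable DLT-free records at assumed rates of 10%/5%, 15%/8% and 20%/10%, against 1.4%, 5.6% and 12.1% for the 50% line.

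The cost is a few sentences and an occasional extra replacement participant.
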